randomized, double blind, placebo-controlled, single switch-over trial of TPTD in premenopausal women with IOP. Forty-one subjects will be assigned to TPTD (Group A; n=28) or placebo (Group B; n=13). At the 6 month timepoint, all subjects will receive TPTD, but blinding of original group assignment will be maintained for an additional 6 months. At the 12 month visit, the blind will be broken and those initially randomized to TPTD (Group A) will continue on study drug for an additional 12 months while those initially randomized to placebo (Group B) will continue for an additional 18 months, so that subjects in both groups complete 24 months of treatment overall. aBMD by DXA and HRpQCT will be measured at baseline and at 6 month intervals. vBMD by cQCT will be performed before randomization and after 24 months of TPTD (Table 1). A quadruple labeled transiliac crest bone biopsy will be performed at 3 months for both Group A and B. Eli Lilly & Company will provide TPTD and placebo but will supply no other funding. After 24 months of treatment in either Group A or B, all women will be offered three choices for follow up: the subjects can A) continue to to be followed for 12 months off TPTD B) choice to leave the study and be treated clinically using an anti-resorptive medication to maintain gains in bone density after treatment with TPTD, or C) join a new study to maintain gains in bone density after treatment. The new study is currently in the design phase and funding phase and precise details are not yet available.

Statistical Analysis Plan

2.A. Statistical Analysis Plan Our aims in this protocol are as follows:

Aim 1: To establish the efficacy and safety of 6 months of TPTD versus placebo in premenopausal women with IOP

Aim 2: To determine the effect of 3 months of TPTD on bone remodeling at the tissue level and the extent to which baseline and 3 month bone remodeling predicts response to TPTD in premenopausal women with IOP.

Aim 3: To determine the extent to which 12 and 24 months of TPTD improves areal and volumetric BMD, bone microarchitecture and strength (stiffness) compared to baseline measures in premenopausal women with IOP

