Visit 2 (Imaging): If the SOPEval is normal, candidates will be invited to proceed with Visit 2. Prior to initiation of any additional study procedures, an informed consent discussion will take place. Only after the informed consent (Study Consent Form) is signed will further research related procedures commence. The study will be described, including the bone biopsy procedure. Participants with fractures will be asked to bring verification (x-rays or radiology reports). They will complete standardized questionnaires to assess current diet and physical activity. We use the validated Block food frequency questionnaire (FFQ; Appendix 3)^{47,48} to assess calcium intake. Physical activity is assessed by the modified Baecke questionnaire (Appendix 4)⁴⁹⁻⁵¹. Equivocal VFA results will be evaluated with spine x-rays. Central QCT of the spine (L1 and L2) with additional single slice at L4, and HR-pQCT of the distal radius and tibia will be performed to measure volumetric BMD, body composition (subcutaneous and visceral adiposity), and cortical and Tb microstructure. Serum will be archived at -80°.At this visit, subjects will also receive tetracycline for their first round of antibiotic labeling and instructions with a scheduled dosing according to protocol. Subjects will complete labeling before the randomization visit, where they will receive Forteo and begin treatment.

52,53

Visit 3 (Randomization): During this visit, imaging results will be reviewed with the subjects. Eligible subjects who agree to participate will be randomized to TPTD or placebo (ratio 28:13) through block randomization with randomly varying block sizes of 2, 4 or 6, stratified by whether they are included on the basis of history of fractures or low BMD. Serum/urine will be archived at -80°C for batch analyses of specialized biochemistries. DNA will be obtained from peripheral blood lymphocytes for archival purposes. We will collect blood for the measurement of osteoblasts, or bone building stem cells, in the bloodstream.

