Subjects will be provided with calcium (citrate) caplets (Citracal + D; each 315 mg + 250 IU D) and a multivitamin (Centrum) that provides 500 IU of vitamin D daily. Most subjects will be instructed to take 2 Citracal caplets and a multivitamin; the total daily dose of calcium from supplements will be approximately 630 mg and of vitamin D 1000 IU. Subjects with very low dietary calcium intake (<500 mg/d estimated by interview and the FFQ), will be asked to take 3 Citracal caplets, while those with high dietary calcium intakes (>1,000 mg/day) will be asked to take 1 Citracal caplet.

Visits 4-5, 8-13 (Study Evaluations): At each study visit, study coordinators will assess any adverse events that transpired since the last study visit. Patients will be instructed to bring their Forteo journal and pens with them to every visit, which documents their compliance with the study medication. The purpose

of the 1-week and 1-month visits (Visits 4 & 5) is to monitor for compliance and adverse effects. At the 1-week and 1-month visit, we will also obtain fasting serum for serum calcium (safety) and at the 1-Month we will also collect serum for BTMs. These visits may be conducted on site for women who reside close to the study sites or may be a telephone contact and local blood draw for those who live at a distance. The remainder of the study visits to perform imaging studies and/or blood draws and dispense study drug are shown in Tables 1-3. We will perform a single follow-up cQCT scan after 24 months of TPTD treatment to minimize radiation exposure in these women who are of child-bearing age. At Visit 12, subjects will be presented with three options for post-TPTD follow up as described in the study design.

Visit 6 (Pre-Biopsy Clearance and Labeling): Subjects will have a pre-biopsy clearance visit with the surgeon and have safety bloods drawn and processed as per hospital regulations. Subjects will receive their second antibiotic labeling agent, demeclocycline, and accompanying labeling schedule.

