MD Visit		X	V	X	X				
Dispense TPTD		X	X X	X					
Telephone Contact [#]	X	X	X X	X	X				
Pregnancy Test BMD by DXA		X	X X	X	X				
History & Physical		X	Λ	X	X				
Adverse Events	v	X	Х	X	X				
Serum FSH	X	X	Λ	X	X				
HR-pQCT		x		X	X				
Central QCT		Λ		X X	Λ				
VFA by DXA		x		X	x				
		X	X	X	X				
Calciotropic Hormones		X		X	X				
Bone Turnover Markers		X	Х	X	X				
* Only for treatment									
treatment (Group A # Will occur before		luled visi	t						

Table 3: Study Visits – Group B**	9 9M	9 12M	10 18	11 24	12 30	13 42
Group D	>	12111	M	M	M	M
MD Visit		х		Х		Х
Dispense TPTD		Х	Х	Х		
Telephone Contact [#]	Х	X	Х	Х	Х	Х
Pregnancy Test		х	х	х	Х	Х
BMD by DXA		х	Х	Х	Х	Х
History & Physical		х		Х		Х
Adverse Events	х	х	Х	Х	Х	Х
Serum FSH					Х	
HR-pQCT			х		Х	Х
Central QCT					Х	
VFA by DXA		х		х		Х
Blood/Serum Archive	х	х	х	х	Х	Х
Calciotropic Hormones		х		Х		Х
Bone Turnover		х	Х	Х	Х	Х
Markers						
** Only for treatment group that started with 6 months of						
placebo injections (Group B)						

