primate macaque was treated with the same toxicity $protocol^{61}$. To date, two cases of osteosarcoma have been reported in among almost 430,000 patients treated with TPTD⁶²⁻⁶⁴; this is approximately the same incidence as the 1.7 patients expected to develop osteosarcoma by chance alone, given an expected incidence of 4-5 per million. An additional case recently reported in abstract form, had osteosarcoma before TPTD was initiated⁶⁵. Moreover, the pathology of the first case was controversial and the second case developed in a man who had received pelvic radiation for prostate cancer and the cancer developed within the field of radiation, rather than in the long bones, as is typical of sporadic osteosarcoma⁶⁴. Among the millions of individuals with hyperparathyroidism who are exposed to chronically elevated levels of PTH, there are only rare reports of osteosarcoma, most of which have not been welldocumented⁶⁶. There were no reports of osteogenic sarcoma among the participants in any of the clinical trials with PTH, amounting to over 2500 patients. In the largest clinical trial with 1637 subjects, there was no increase in cancer incidence between subjects receiving TPTD and placebo and no woman developed an osteosarcoma²⁸. Given all these considerations, it appears that, in general, PTH is safe in humans and that TPTD will be a safe treatment for premenopausal women with IOP. Nevertheless, it is important that subjects in this study are informed of the rat toxicity data and the case reports. Consistent with FDA guidelines, no patient will receive active drug for more than 2 years. In addition, the dynamic histomorphometry measurements we will have will offer an extra measure of safety parameters. We plan to minimize the already small risk by excluding adolescents who may not have fused epiphyses and women with a history of skeletal radiation.

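### Table 2 as extracted marks teriparatide dispensing for Group A at 24M, when the stated 24-month course and 2-year limit have been reached

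*Combined protocol and SAP*

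**What the plan says.** **Course length.** Section 2 sets the schedule "so that subjects in both groups complete 24 months of treatment overall". From the 12-month visit, when allocation becomes known, the rule for the first group is that "those initially randomized to TPTD (Group A) will continue on study drug for an additional 12 months". Group B is given 18 months from the same point. Section 3.A (Visit 2) places the start of treatment at randomization: "Subjects will complete labeling before the randomization visit, where they will receive Forteo and begin treatment".

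**Exposure limit.** Section 11, in the osteosarcoma paragraph, says that "no patient will receive active drug for more than 2 years".

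**End of treatment.** Section 3.A (Visits 4-5, 8-13) says: "At Visit 12, subjects will be presented with three options for post-TPTD follow up". Visit 12 is headed 24M in Table 2 (Group A) and 30M in Table 3 (Group B).

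**Dispensing.** The same paragraph of Section 3.A points to Tables 1-3 for the visits at which study drug is given out. The row "Dispense TPTD" is marked as follows:
- Table 1: randomization, 3M and 6M.
- Table 2 (Group A), as extracted: 12M, 18M and 24M; blank at 9M and 36M.
- Table 3 (Group B): 12M, 18M and 24M; blank at 9M, 30M and 42M.

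**The concern.** The prose and Table 2 give different answers to one question: does Group A receive drug at the visit that ends its course? The text says that treatment is complete and that the women now choose what follows. The table says to dispense. For Group B, at the visit that marks the same milestone, the table agrees with the text.

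This matters because staff dispense from the tables. Someone following Table 2 would hand out active drug to women who had already reached a limit that the protocol presents as a safeguard. Table 2 has no visit between 24M and 36M, so use of that supply would fall in a stretch with no scheduled assessment. A woman who chose the 12-month observation would also not be off teriparatide for all of it.

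**Working it through.** **1. Reproduce the stated course.** Inputs are from Section 2.
- Group A: 12 months up to the 12-month visit + 12 further months = 24 months, reached at study month 24.
- Group B: (12 − 6) + 18 = 24 months, reached at study month 12 + 18 = 30.

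Both agree with the 24 months stated.

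**2. Set completed exposure against the dispensing marks.** Months of active drug are the study month for Group A, and the study month minus 6 for Group B.

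| Visit | Group A: months completed | Table 2 | Group B: months completed | Table 3 |
|---|---|---|---|---|
| 12M | 12 | marked | 6 | marked |
| 18M | 18 | marked | 12 | marked |
| 24M | 24 | marked | 18 | marked |
| 30M | no visit | – | 24 | blank |

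Group B's last dispensing falls at 18 months of active drug. Group A's falls at 24.

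**3. Is there a treatment interval for a 24M supply to cover?** Neither Table 2 nor Table 3 marks dispensing at 9M, so the 6M supply has to last until 12M, which is 6 months. The steps from 12M to 18M and from 18M to 24M are also 6 months. On that spacing the 18M supply runs to the end of Group A's course, and a 24M supply has no planned interval left.

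**4. Is the 24M mark real?** Table 2 was damaged in conversion, so this needs its own check.
- *Position.* The dispense row lies above the first visible merger (pregnancy test with BMD). At 36M the MD visit, dispense and telephone rows read marked, blank, marked. At 9M they read blank, blank, marked. Blanks therefore survived in this part of the table. At 24M all three are marked.
- *Column counts.* Table 3 lists 14 procedure rows. Counting clear X marks in Table 2 gives 12 at 12M, 14 at 24M and 11 at 36M. Fourteen means that every row, dispensing included, is marked at 24M. Twelve fits a 12M visit without FSH or central QCT. Eleven fits a 36M visit without dispensing, FSH or central QCT.

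**5. Size.** Group A is 28 of the 41 planned subjects: 28/41 = 68%, before any drop-out. The quantity dispensed at a visit is not stated. Assuming that the whole supply is used:
- 1 month: 24 + 1 = 25 months
- 3 months: 24 + 3 = 27 months
- 6 months (the spacing in step 3): 24 + 6 = 30 months

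**6. Reach into the analyses.** Aim 1 is analysed at 6 months. Aim 2 uses the 3-month biopsy and bone density changes at 12 and 24 months. Aim 3 uses 12 and 24 months of teriparatide. No analysis in Section 2.A uses 36M data, and drug handed out at the 24M visit cannot change what is measured at that visit. No power statement in Section 2.B depends on it.

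**The case against.** The strongest objection is that the contradiction rests on one cell of a damaged table. In the same row the 18M cell reads as two marks, which one row cannot have, and the table's footnote is cut off. The column counts are not clean either:
- 18M shows 9 clear marks where about 7 would be expected.
- The 24M total of 14 needs both marks in a doubled central QCT cell.
- The 36M total of 11 leaves out a stray character in the central QCT row.
- The FSH row is marked at 9M, 12M and 36M, which suggests that rows below the merger have slipped.

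This stands as far as it goes. The counts are supporting evidence only, and the original page has to be looked at. It does not remove the reading, because the dispense row sits above the merger with its 9M and 36M blanks intact.

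A second objection is that the prose is unambiguous and the blind is broken at 12 months, so staff would know that a Group A woman had finished. The prose is indeed clear. But Section 3.A sends staff to the tables for dispensing, and the tables are where the error would act.

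Third, Table 3 does not reverse Table 2. Both mark the same calendar months, and Group B's six-month later start on active drug makes those months fit its course. Carry-over of calendar months from one table to the other is a possible cause, but the documents do not confirm it.

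A reader might also infer that women were over-exposed, or that the trial's results are compromised. The documents show neither. They give no dispensing records and no supply quantity. The 36M visit feeds no planned analysis, and observation is only one of three choices at Visit 12.

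**Conclusion.** This is an internal contradiction and, if the mark is confirmed, Table 2 is wrong as written against the protocol's own text. It touches a stated safety limit in the schedule that staff are told to use, so it is more than a clerical slip and should be corrected.

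Its reach is up to 28 Group A women. The excess over 24 months cannot be fixed from the documents: 25 to 30 months in total under the assumed supplies of 1 to 6 months. That range assumes that the mark is genuine, that the supply is fully used and that no one has dropped out. Group B is not affected. Beyond exposure, the only consequence is that women choosing the 12-month observation would not be off drug for all of it. If the original page shows a blank cell, the point falls away.

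**What to change.** 1. Check the 24M cell of the Table 2 dispense row on the original page.
2. If it is marked, reconcile the row with the 24-month course in Section 2, the post-treatment options at Visit 12 in Section 3.A, the 2-year limit in Section 11, and the treatment of Group B's 30M visit in Table 3. The sponsor states which of these governs.
3. Notify the research pharmacy of the outcome.

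The cost is one table cell and one notification, plus the IRB approval and the DSMB and FDA notices that Sections 12 and 17 already require for protocol changes. No procedure, sample size or analysis changes.

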# Will occur before the scheduled visit						

For the sub-study: This sub-study involves only one visit that can be done at the same time as a visit completed for the main study. Four blood draws will be performed. These bloods will be collected while subject is fasting. The first blood draw will be collected right before the subject completes the Forteo injection. These will be considered the baseline bloods. The remainder 3 blood draws will be collected 30 minutes after injection of Forteo, 60 minutes after Forteo injection and 4 hours after Forteo injection. Samples will be stored for measurement of drug (Forteo: PTH1-34) and drug effects (calcium).

3.B Study Procedures

1. BMD by DXA: Areal BMD (aBMD) of the LS (L1-4), proximal femur and non-dominant forearm will be measured at CUMC on Hologic QDR 4500 densitometers (Hologic, Inc., Waltham, MA). Dedicated technologists, certified by the International Society of Clinical Densitometry, with long-term research experience perform all scans. Phantoms are scanned daily to check for detector drift; the results are appended to a quality control (QC) database. Results are downloaded to specific project databases. The effective dose for BMD by DXA is7.45 μ Sv.

2. Body Composition by DXA: Total fat mass, lean mass, and percent fat mass will be measured by DXA. The effective dose for whole body DXA is 5.2 mrem. Our precision is 1%.

3. Vertebral Fracture Assessment (VFA) by DXA: Visual semiquantitative identification of vertebral fractures is obtained from images acquired by fan-bean DXA scanners. VFA demonstrates good agreement with conventional radiographs (96.3%, k=0.79) in classifying vertebrae as normal or deformed. With its low radiation and good precision, VFA is useful to identify subjects with and without vertebral fractures. The total effective radiation dose associated with each VFA 5.2µSv.

4. High Resolution Peripheral Quantitative Computed Tomography (HR-pQCT): HR-pQCT is performed on the XtremeCT (Scanco Medical AG, Switzerland). The nondominant distal radius and tibia are immobilized in a carbon fiber shell (158-160). The region of interest is defined on a scout film by manual placement of a reference line at the endplate of the radius or tibia; the first slice is 9.5 mm and 22.5 mm proximal to the reference line at the radius and tibia respectively. A stack of 110 parallel CT slices is acquired at the distal end of both sites using an effective energy of 40 keV, slice thickness of 82

 μ m, image matrix size 1024x1024, nominal voxel size of 82 μ m. This machine provides a 3D image of 9 mm in the axial direction. HR-pQCT provides microstructural information (cortical and trabecular density, cortical thickness, trabecular number, thickness and separation) previously obtainable only by an invasive bone biopsy. We are one of only 5 US medical centers with this new technology. For HRpQCT of the forearm and leg, the estimated effective whole body dose is below 5 μ Sv per scan, since only a very small fraction of the distal forearm or leg is irradiated.

5. Volumetric BMD by Central OCT: Volumetric OCT acquisitions of the L1-L2 vertebrae (80 kVp, 140 mAs, 2.5 mm slice thickness, pitch=1.2, standard reconstruction algorithm, 3-Bar Image Analysis QCT Calibration Phantom (Image Analysis, Columbia, KY) will be carried out on a Siemens Biograph 40 Slice CT Scanner (Siemens Medical Solutions, Malvern, PA), located within CUMC's Kreitchman PET/CT Center. Scan data are archived to CD and forwarded to a central analysis site (UC San Francisco, Dept. of Radiology) for scan quality assurance and analysis. Spine CT images are analyzed with image analysis software developed by our collaborator and consultant, [name]. L1-L2 measures analyzed by this software include vBMD of an integral compartment containing the vertebral body and posterior elements (viBMD), the areal BMD of this region obtained by computing its bone mineral content and dividing by the projected area in the AP plane (QCTaBMD), and the vBMD of a region containing almost all of the trabecular bone in the vertebral centrum (vtBMD). BMD data obtained on each scanner are converted to the calibration-phantom equivalent BMD. To ensure comparability of data obtained on different CT scanners used at CUMC, CT data are cross-calibrated using the Image Analysis Torso Quality Control phantom (Image Analysis, Columbia, KY) which is scanned multiple times on each system. Total effective radiation dose from a central QCT scan of the spine is estimated at $470 \,\mu$ Sv which is equivalent to approximately 2-3 months of background radiation (assumed to be 3 mSv/year).

6. Body composition by CT: At the time that L1-L2 cQCT measures are acquired, as above, one additional axial image slice (10mm thick) will be obtained at the mid L4 vertebra level⁷⁷. Based upon this image, the cross-sectional areas of visceral adipose tissue (VAT) and subcutaneous adipose tissue (SAT) in cm² will be calculated by the method of Zhao et al ⁵⁴. The additional radiation exposure from the single slice is estimated to be 10% of the exposure for the L1-L2 scan above (approximately 5µSv).

7. Spine Radiographs: Lateral thoracic and lumbar spine radiographs for diagnosis of prevalent or incident vertebral fractures, performed using the protocol used in the Study of Osteoporotic Fractures (SOF) ⁵⁵, will be used in subjects for whom VFA diagnosis of fractures is ambiguous. Total critical organ absorbed dose from a lateral thoracic and lumbar spine radiograph is equivalent to about 350 mrem. Our skeletal radiologist, [name]., evaluates and reads these x-rays.

8. Biochemical Assays: All blood samples will be collected fasting in the morning. General tests (CBC, serum calcium, phosphate, albumin, renal and liver function tests, urine calcium and creatinine) will be run when collected by standard methods. Serum for PTH, 25-OHD, 1,25(OH)₂D, osteocalcin, BAP, P1NP, CTx, IGF-I, IGFBPs, leptin, adiponectin, insulin, glucose, IL-6, homocysteine, c-reactive protein (CRP), lipid studies, E2, testosterone, SHBG, OPG, RANKL will be aliquoted, frozen immediately and stored at -80°. Specimens will be shipped frozen from the CORC to Columbia. Additional serum/urine will be archived for measurement of BTMs and mineral metabolites that may become available in future. Blood for DNA will be obtained from peripheral blood lymphocytes for archival purposes. We intend to isolate and store these samples for future genetic studies that may identify a polymorphism linked to one of our phenotypes, or identify a new candidate gene polymorphism in our study population. Blood for osteoblasts, which are bone-building stem cells, found in the bloodstream, will be collected. These will be processed and stored frozen at -80°C. All assays are currently in place either in the CUMC Bone Marker Laboratory within the Division of Endocrinology, under the direction of [name]., PharmD or

the Core Laboratory of the Irving Institute for Clinical and Translational Research (CUMC CTSA). Lipid particle size analysis will be conducted at Liposcience, Inc.

9. Bone Biopsy of Iliac Crest: Transiliac crest bone biopsy will be performed according to procedures established at CPMC and CORC. Participants will receive instructions and medications for tetracycline and demeclocycline "quadruple labeling" at the beginning of the study and one month prior to second label. Transiliac crest bone biopsy will be performed according to standard procedures established here at CUMC and Creighton University under the direction of Drs. [name] and [name], who both have long track records of performing successful research quality bone biopsies. Bone biopsies will be performed by [name], [name] or [name] in the Milstein Operating Rooms at CUMC. The biopsy sample will be placed in a 30 ml liquid scintillation vial containing 70% ethanol and shipped to [name] [name]'s laboratory for microCT and FEA. Next, the specimens will be shipped to [name] laboratory (Helen Hayes Hospital, West Haverstraw, NY) for embedding and analysis.

4. Study Drugs or Devices

Teriparatide has been FDA approved for the treatment of osteoporosis since November 2002. The pen delivery device will be fully coded and ready for distribution by our research pharmacy. Two identical sets of pens will contain placebo (vehicle alone) or 20 mcg of teriparatide. Drug will be stored in a refrigerator in the research pharmacy until it is dispensed. Subjects will be instructed to refrigerate the medication at home during their pen training.

The study drug will be packaged in a pre-filled pen delivery device (20 mcg or placebo in 3 ml) in such a manner as to make active and placebo TPTD indistinguishable. Each pen will be labeled with the subject identifier and the 24-hr telephone number of the research pharmacist who will retain information of treatment allocation in the event that unblinding becomes necessary. All other study related items and documents are only identified with the subject identifier. All subjects will be trained to self-administer agent (drug or placebo) by our research nurse. All medication will be dispensed by the research pharmacy of the Office of Clinical Trials at Columbia University.

5. Study Instruments

Subjects will complete the following standardized questionnaires as part of this protocol.

- 1. Historical Questionnaire on medical and reproductive history (menstrual history, menarchal age, parity, OCP use), risk factors for osteoporosis (eating disorders, alcohol, tobacco, caffeine intake), personal and family history of fractures, current and past medications.
- 2. Dietary Rapid Calcium Assessment to assess calcium intake
- 3. The Eating Disorder Examination Questionnaire (EDE-Q) to screen out subjects with a current eating disorder
- 4. Block Food Frequency Questionnaire (FFQ) to assess dietary habits
- 5. Modified Baecke Questionnaire to assess physical activity
- 6. Phone Screening Questionnaire

Questionnaires 2-4 are all validated, standardized instruments. These questionnaires are all attached in the RASCAL system.

